8.7.5 Duration of treatment and reasons for discontinuation

Summary statistics for the duration of Kineret treatment will be presented overall and by time window.

The reasons for Kineret treatment discontinuation for more than 30 days will be summarized with number and percentage. The reasons for discontinuation will be collected as per the Pharmachild CRF: adverse event (moderate/severe/serious event or mild event), intolerance, dose change, inefficacy, remission, surgery, pregnancy or other reason. A patient can contribute with multiple discontinuations if starting a new treatment period after a treatment holiday of more than 30 days. Furthermore, multiple reasons can be recorded for one single discontinuation

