SJIA is an autoinflammatory disease, characterized by chronic arthritis, high spiking intermittent fever, maculopapular rash, hepatosplenomegaly, lymphadenopathy, serositis, and marked increase in acute-phase reactants (1-3). SJIA is associated with complications, including joint damage, growth impairment, osteoporosis, amyloidosis and the potentially fatal MAS (4-8). Laboratory and clinical observations suggest an inappropriate activation of the innate immune system, with hypersecretion of the proinflammatory cytokines interleukin-1 (IL-1) and 6 (IL-6).

Kineret[®] is a human IL-1 receptor antagonist that has been approved in the EU for treating signs and symptoms of rheumatoid arthritis since 2002 and CAPS since 2013. In 2018 the European Commission approved Kineret in adult and pediatric patients for the treatment of Still's disease, including SJIA and AOSD, with active systemic features of moderate to high disease activity, or in patients with continued disease activity after treatment with NSAIDs or glucocorticoids. Kineret can be given as monotherapy or in combination with other anti-inflammatory drugs and DMARDs.

As agreed with EMA, the study is designed to further investigate long-term safety and potential risk for MAS in patients with SJIA treated with Kineret. This non-interventional PASS was included in section III.2-3 of the EU RMP as a category 3 activity.

The protocol for this study is developed in accordance with the EMA guidance for the format and content of the protocol of a non-interventional PASS (9). The study will be registered in the public EU PAS register and on clinicaltrials.gov. The collected safety data will be reported in PSUR and RMP updates where applicable.

7 Research question and objectives

The objective of the study is to evaluate and characterize the long-term safety profile of Kineret treatment when used in standard clinical practice to treat patients with SJIA, including the occurrence of MAS as an ESI.

The endpoints to support the objective for the study are:

- The occurrence of non-serious AEs of at least moderate severity and serious AEs (SAEs), including MAS as an ESI.
- The duration of Kineret treatment in a real-world setting.
- The reasons for Kineret treatment discontinuation.

8 Research methods

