8.2 Setting

Data will be extracted and analyzed for all male and female patients with a diagnosis of SJIA as per the ILAR classification criteria (10, 11) included in the Pharmachild registry and who were ever treated with Kineret subsequently to SJIA diagnosis.

That is, all eligible patients participating in the Pharmachild JIA registry study are included in this study. No specific exclusion criteria will be applied.

No treatment assignment or randomization is applicable.

This study is based on secondary use of data from the Pharmachild registry. The Pharmachild registry was set up in December, 2011. Both retrospective and prospective data has been collected within the registry. The first Kineret treatment, retrospectively collected in the registry, occurred in 2004. Data collected in the registry up until September 30, 2018 will be used in this study. The data extraction from the registry will start in March, 2019 and end in April, 2019.

40 countries participate in the Pharmachild JIA registry. 15 of these countries have collected data from patients meeting the above criteria; Croatia, Denmark, France, Germany, Greece, Hungary, Israel, Italy, Latvia, Netherlands, Norway, Romania, Saudi Arabia, Spain and Switzerland.

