8.4 Data sources

PRINTO (www.printo.it) is a non-profit, non-governmental, international research network founded by [name] and [name] in 1996 (12). PRINTO initially included 14 European countries (now 88 countries, 640 centers worldwide with 1348 members today), with the goal to foster, facilitate and co-ordinate the development, conduct, analysis, and reporting of international, multi-center, clinical trials and/or outcome standardization studies in children with paediatric rheumatic diseases. PRINTO governing bodies are the advisory council, the national coordinators and the International coordinating center based in Genoa, Italy at the IRCCS G. Gaslini hospital.

The Pharmachild JIA registry, which was set up in December, 2011 with a 3-year grant from EU and is maintained by PRINTO, is a registry collecting data from patients with JIA including patients with SJIA. In the Pharmachild JIA registry 40 countries are participating of which 15 countries have collected data on Kineret treatment: Croatia, Denmark, France, Germany, Greece, Hungary, Israel, Italy, Latvia, Netherlands, Norway, Romania, Saudi Arabia, Spain and Switzerland. The data used in this study will hence be collected from these countries.

The Pharmachild JIA registry study has obtained the ENCePP Study Seal. ENCePP is a collaborative scientific network coordinated by the European Medicines Agency (EMA) and developed in collaboration with European experts in the fields of pharmacoepidemiology and pharmacovigilance. The ENCePP Study Seal means that a study upholds high standards throughout the research process based on the principles of transparency and scientific independence.

As per August 20, 2018 the data source contains both retrospective and prospective data as follows (Table 1).

Table 1

Data type	Number of JIA patients	Number of SJIA patients	Number of SJIA patients treated with Kineret
Only retrospective data	5208	587	212
Retrospective + Prospective data	3508	352	95
Total	8716	939	307

The retrospective data are the data collected from the medical records prior to enrollment in the Pharmachild registry. The prospective data are data collected after enrollment in the registry. For this study retrospective and prospective data will be treated equally.

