This study is based on secondary use of data already available in the Pharmachild registry. The source for all data in the registry is the patients' medical records. In the registry both the retrospective and prospective part contain demographics, concomitant medications since onset of disease until last available follow up, AEs that are of at least moderate severity and events of special interest (e.g. MAS). AEs are coded in MedDRA version 21.1. A medical monitor evaluates all reported AEs. This person can raise queries to the centers and request further clarifications.

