8.5 Study size

The sample size is not based on any formal calculation. All patients enrolled in the Pharmachild JIA registry study before September 30, 2018 meeting the criteria defined for the study population will be included in the study.

It is estimated that approximately 300 patients may be included.

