8.7.2.3 Kaplan-Meier cumulative probability curve of MAS

The cumulative probability of a first event of MAS over time will be estimated for the complete set and graphically presented as a Kaplan-Meier curve.

In addition, a Kaplan-Meier cumulative probability curve stratified by history of MAS at baseline (Yes/No) will be presented. In the case of too few patients in either of the subgroups (number of patients ≤ 10), the stratified analysis should be dismissed from the CSR.

Patients should be censored at 2 days after discontinuation of Kineret treatment, if they die for other reasons than MAS (no 2 days addition), if they are lost to follow-up, or if they have still not experienced a MAS event at the last visit.

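### Section 8.7.5 analyses the treatment-duration endpoint by summary statistics alone, with no censoring of courses still running when observation ends

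*Protocol*

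**What the plan says.** Protocol Section 7 lists three endpoints, one of which is "The duration of Kineret treatment in a real-world setting". The only analysis stated for it, in Section 8.7.5 and in the same terms in the abstract, is "Summary statistics for the duration of Kineret treatment will be presented overall and by time window". The time windows are those of Section 8.7.1: four of six months each, then an open one beyond 24 months.

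Several places fix where observation stops:

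- Section 8.2: "Data collected in the registry up until September 30, 2018 will be used in this study".
- Section 8.4 describes the medication record as "concomitant medications since onset of disease until last available follow up".
- Section 8.4 also states: "The retrospective data are the data collected from the medical records prior to enrollment in the Pharmachild registry". Table 1 has the row "Only retrospective data 5208 587 212"; the last figure is the number of Kineret-treated SJIA patients with no prospective data.
- Section 8.5 admits patients enrolled up to the cut-off, with no minimum follow-up, and says "It is estimated that approximately 300 patients may be included".

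For first MAS, Section 8.7.2.3 specifies a Kaplan-Meier curve. It censors patients at loss to follow-up, "or if they have still not experienced a MAS event at the last visit", among other reasons. Section 8.7.5 has no counterpart to this, and the limitations in Section 8.9 do not mention unfinished courses.

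**The concern.** A child who is still on Kineret when the record ends has a treatment duration known only to exceed the observed time. A mean or median of observed lengths treats that course as if it had stopped on that day. Leaving such courses out is worse, because short courses are more likely to have finished in time to be counted.

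Either way, the answer to a named endpoint would depend partly on enrolment dates and the data cut-off rather than on how the drug is used. The split by time window does not help, since duration within each of the first four windows cannot exceed about six months. Section 8.7.5 also does not ask for the number of courses still running, so a reader of the report could not judge how far the figure falls short.

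**Working it through.** **Inputs from the protocol.** Table 1 (Section 8.4) adds up: 5208 + 3508 = 8716, 587 + 352 = 939, 212 + 95 = 307. Retrospective-only patients are 212/307 = 69%. The total of 307 agrees with the estimate of about 300 in Section 8.5. The protocol states no duration and no share of running courses, so there is no figure of its own to reproduce.

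**Where observation ends.** It ends at the cut-off, at the last follow-up, or, for the 212, no later than enrolment. None of these points is tied to the end of treatment.

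**Direction.** Let T be the true course length and Z the time from start of treatment to the end of observation. The observed length is min(T, Z), which is never greater than T. Completed courses are those with T ≤ Z, which favours small T. Both summaries are therefore biased short whenever some courses are running.

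**Size, by assumption.** Assume a true median of 24 months and Z uniform on 0 to C months, independent of T. For exponential T with rate λ = ln 2/24 = 0.0289 per month:

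- share running: p = (1 − e^(−λC))/(λC)
- median of observed lengths: the t that solves e^(−λt)(1 − t/C) = 0.5

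With C = 60, λC = 1.733 and p = (1 − 0.177)/1.733 = 0.475, or 48%. At t = 14.5 the left side is 0.658 × 0.758 = 0.499, so the median of observed lengths is about 14.5 months against a true 24. With C = 36 it is 11.2 months (62% running), and with C = 120 it is 18.3 months (28% running).

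A simulation of 300 patients with 1000 replicates set C to give a chosen share running, with Weibull shape 0.7 and 1.0 (exponential). Each cell shows shape 0.7 / shape 1.0. Shortfall is (24 − median of all observed lengths)/24.

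| Running | Median, all observed lengths (months) | Shortfall | Median, completed only (months) | Kaplan-Meier median (months) |
|---|---|---|---|---|
| about 0% | 24.2 / 23.9 | about none | 24.2 / 23.9 | 24.4 / 24.0 |
| 10% | 21.9 / 21.8 | 8.8% / 9.2% | 20.1 / 21.6 | 24.1 / 24.1 |
| 20% | 19.9 / 19.8 | 17.1% / 17.5% | 16.3 / 19.0 | 24.1 / 24.1 |
| 30% | 17.8 / 17.9 | 25.8% / 25.4% | 13.0 / 16.3 | 24.2 / 24.1 |
| 40% | 15.4 / 16.0 | 35.8% / 33.3% | 10.1 / 13.8 | 24.5 / 24.1 |
| 50% | 12.7 / 14.0 | 47.1% / 41.7% | 7.5 / 11.2 | 24.2 / 24.1 |
| 60% | 9.9 / 11.7 | 58.8% / 51.3% | 5.3 / 8.8 | 24.1 / 24.2 |

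At 60% running with shape 0.7, the Kaplan-Meier median was not reached in 4% of replicates.

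In this model T and C scale together, so the percentage shortfall depends on the share running and the shape, not on the choice of 24 months. This matters for the 10% row. With a 24-month median and shape 1.0 it needs C = 346 months, but at most 177 months lie between January 2004 and September 2018 (Section 8.2 dates the first recorded Kineret treatment to 2004). With a 12-month median the same row needs C = 173 months.

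**The case against.** The strongest reply is that this is SAP material. Annex 1 lists a separate SAP, which is not at hand. The term summary statistics does not exclude a Kaplan-Meier median, and the handling of courses without a stop date is often left to that document. This stands in part: a reader might infer that the protocol tells the analyst to count running courses as finished or to drop them, and it does not say so. But the protocol does choose methods. It names Kaplan-Meier with censoring rules for MAS and summary statistics for duration, and the natural reading of the second is a mean, median and range of observed lengths.

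A reader might also infer that many courses are running, or that the 212 retrospective-only patients are the censored ones. The documents support neither. Inclusion requires only that the patient was ever treated, and treatment goes back to 2004, so an unknown share of courses ended well before enrolment. The figure of 212 says where records stop, not who was on the drug at that point.

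It can also be said that observed time on drug is the right context for the safety rates, which Section 8.7.1 bases on observed patient-time. That stands in full. The sets with at least 12, 18 and 24 months of continuous treatment (Section 8.7) also give a partial view of persistence. Neither provides an estimate of how long treatment lasts.

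Finally, a reader might want the cumulative incidence of stopping by reason. Number and percentage already answer the endpoint on reasons. Section 8.7.5 allows several reasons for one stop, so the extra analysis would need a priority rule. It is optional and not part of this point.

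**Conclusion.** The point holds in conditional form. Unfinished courses are expected from the design, the protocol's only stated analysis of duration makes no provision for them, and ordinary summaries of observed lengths would be biased short. The direction is certain wherever some courses are running and are entered at observed length or left out.

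The size cannot be read from the documents. It ranges from almost nothing with hardly any running courses to 51 to 59% of the median at 60% running, under Weibull stopping times and uniform independent censoring. The documents do not support an unconditional statement that real-world duration is understated by a given amount, nor any claim that the adverse event rates are affected. The correction is worth making because duration is a named endpoint and the change is cheap.

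**What to change.** In Section 8.7.5, replace the sentence on duration with text to this effect: time from the start of the first Kineret course to the first discontinuation of more than 30 days will be estimated by Kaplan-Meier, with courses ongoing at last follow-up or at the 30 September 2018 cut-off censored there. Report the median with 95% CI, the proportion still on treatment at 6, 12, 18 and 24 months, and the number of ongoing courses. Keep the summary statistics of observed time, including restarts, as a separate row labelled observed exposure. Carry the same wording into the abstract.

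The cost is one protocol paragraph and one table or figure, from start and stop dates already needed for exposure time in Sections 8.7.1 and 8.7.4. The median may not be reached in some subsets, and later courses will appear only in the exposure row. The estimate also assumes that the end of observation is unrelated to the prospect of stopping, which the report should state.

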8.7.6 Concomitant medications

Treatment regimens of DMARDs, biologics and systemic glucocorticoids concomitantly with first dose of Kineret will be summarized by dividing patients in groups of treatment patterns, i.e.

- Kineret only.
- Kineret+MTX.
- Kineret+glucocorticoids.
- Kineret+MTX+glucocorticoids.
- Kineret+other biologics.
- Kineret+other biologics+MTX.
- Kineret+other biologics+MTX+glucocorticoids.
- Kineret+other biologics+glucocorticoids.

In addition, treatment patterns (prescribed treatments) prior to initiating Kineret will also be presented. Categories to present are:

- None.
- MTX only.
- Glucocorticoids only.
- Biologic agents only (other than Kineret).
- Biologic agents other than Kineret+glucocorticoids.
- MTX+glucocorticoids.
- MTX+biologic agents other than Kineret.
- MTX+biologics other than Kineret+glucocorticoids.

Number and percentage of patients within each category of treatment pattern will be presented.

8.8 Quality control

Collection of data has followed standard clinical practice in treatment of the patients. The source for all collected data is the patients' medical records.

It is the responsibility of the Investigators in the Pharmachild registry study to ensure completion and to review all data entered on the PRINTO website. At all times, the Investigators have the final responsibility for the accuracy and authenticity of all patient data entered.

The PRINTO web system is provided with validation control and it is not expected to have missing data related to mandatory questions. All data entered is reviewed by the PRINTO coordinating center for completeness and coherence. If necessary PRINTO personnel contacts the Investigators to verify correctness and consistency of the data and to retrieve missing data if available. In case of discrepancies, specific queries are issued and resolved through a query ticket system. A medical monitor evaluates all reported AEs. Data can be updated or modified by the Investigator only upon request to the PRINTO helpdesk.

Data is validated on an ongoing basis, and a specific validation process is applied.

8.9 Limitations of the research methods

An uncontrolled single-armed study design is the only feasible design in this non-interventional study since a fair comparator group would be difficult to introduce given the real-world practice of treatment regimen. Accordingly, the study design carries the general limitations inherent in an uncontrolled design regarding statistical analyses, interpretation, generalizability and conclusiveness. The incidence rates for AEs while exposed to Kineret may be under or overestimated because of exposure-related misclassification of patient-time. The direction of the bias will depend on the direction of the difference in true incidence in the non-exposed (all other treatment options) group vs. Kineret exposed group (e.g. a higher incidence in non-exposed vs. exposed will over-estimate the incidence rates for the Kineret treatment). The non-exposed patient-time will likely be a mixture of other SJIA-related medications. Misclassification of exposure is likely during non-registered short interruptions of Kineret treatment. Nevertheless, by using a validly conducted register study with the primary objective to research the adverse effects of JIA related medications and with granular recording of exposure time will alleviate the magnitude of the potential exposure misclassification bias.

The use of sub-populations with patients treated for a certain time may bias the comparisons since the selected patients may have been selected because of a relatively low incidence of adverse events before selection into the sub-population. The probability of experiencing an adverse event by chance may be increased following selection into the sub-population. A comparison with the incidence rate for the respective time window in the total population (the complete set) and not only the sub-population specific incidence rate will likely alleviate a more unbiased conclusion.

All patients in the Pharmachild registry with a diagnosis of SJIA (as per ILAR classification criteria) and who were ever treated with Kineret following the SJIA diagnosis will be included in

this study. No other criteria will be used to select patients. In the Pharmachild study a census (e.g. collection of patient identification number, age, JIA type and type of treatment) is required from each centre before retrospective chart review of safety data initiation to avoid selection biases (e.g. to have the proper denominator against which evaluating the successful data collection).

Altogether, the chosen design is deemed acceptable for a study with the primary objective to assess long-term safety of Kineret in patients with SJIA under standard clinical care.

8.10 Other aspects

The relevant aspects of the study are covered in previous sections.

9 Protection of human subjects

This study will comply with the definition of the non-interventional (observational) study provided in Article 2(c) of Directive 2001/20/EC (13), the definition for Post-Authorization Safety Studies in Directive 2001/83/EC Art 1 (14), and its refinement provided in the Guideline of Good Pharmacovigilance Practices (GVP) Module VIII – Post-Authorization Safety Studies (15). This study will be conducted in compliance with the code of Good Pharmacoepidemiology Practices (GPP) (16) and the European Network of Centres for Pharmacoepidemiology and Pharmacovigilance (ENCePP) standards.

This study will be conducted in compliance with this protocol and in accordance with the ethical principles for Medical Research Involving Human Subjects in the Declaration of Helsinki (17) and will be consistent with the International Ethical Guidelines for Biomedical Research Involving Human Subjects and applicable parts of the ICH GCP (18) (19), as well as all other applicable regulatory requirements. This study will be conducted in compliance with the European data protection regulation, GDPR (20).

Study personnel involved in conducting this trial will be qualified by education, training, and experience to perform their respective task(s). The investigator will also ensure that this study is conducted in accordance with the local laws and regulations.

9.1 Research Ethics Review (REB)

All necessary approvals for collection of the data in the Pharmachild registry have been obtained by PRINTO.

The PRINTO network is allowed to share summary data with pharmaceutical companies. Additional approval is needed for sharing of raw data. However, no individual patient listings will be obtained for this study, only summary outputs. Hence no additional approvals are required.

9.2 Informed consent

Not applicable. Patients signed an ICF when entering the Pharmachild registry which includes an approval to share data with regulatory authorities (EMA, FDA or national authorities) and pharmaceutical companies, this without collecting additional consent.

In some of the participating countries a signed ICF is not required to collect retrospective data. This is reflected in the Pharmachild registry which contains more retrospective than prospective data as demonstrated in table 1 in section 8.4

